4.0 Objectives

4.1 Primary Objectives

1. Quantify number of CR, PR, MR, SD and progressions in response to dosimetry-guided PRRT utilizing RECIST 1.1 criteria and ⁶⁸Ga-DOTATOC or ⁶⁸Ga-DOTATATE PET to evaluate efficacy of ⁹⁰Y-DOTATOC therapy in children and adults with neuroendocrine and other somatostatin receptor positive tumors.
2. Monitor renal, hematologic, and clinical toxicities associated with dosimetry-guided ⁹⁰Y-DOTATOC PRRT while maximizing total tumor dose and limiting total renal dose of ⁹⁰Y-DOTATOC to ≤ 23 Gy.

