5.0 Eligibility Criteria

5.1 Inclusion Criteria

1. Disease not amenable to standard treatment (nonresectable or disease present after one or more surgeries and/or Sandostatin treatment) or subject has failed existing first line chemotherapy, biologic therapy, targeted agent therapy or radiation therapy.
2. Participation in Iowa Neuroendocrine Tumor Registry.

3. A pathologically confirmed (histology or cytology) malignant neoplasm with at least one target lesion that is confirmed by conventional imaging and is determined to express somatostatin receptors by ⁶⁸Ga-DOTATOC (TATE) PET within 6 months prior to treatment with ⁹⁰Y-DOTATOC.
4. The target lesion is one that either has never received external beam radiation or has been previously irradiated and has since demonstrated progression. Any local irradiation of the target lesion or any non-target lesions via external beam, conformal or stereotactic radiation treatments must have occurred more than 4 weeks prior to study drug administration. Any full cranial-spinal radiation, whether or not a target lesion is included in the field, must have occurred more than 3 months prior to study drug administration.
5. Life expectancy \geq 2 months at the time of study drug administration.
6. Archival tissue from a previous biopsy will be required.
7. Age \geq 6 months-90 years at the time of study drug administration.
8. Performance status as determined by Karnofsky \geq 60 or Lansky Play Scale \geq 60% at the time of study drug administration.
9. Completion of Norfolk Quality of Life Questionnaire.
10. Within 7-10 days of study drug administration, patients must have normal organ and marrow function as defined below:
 - absolute neutrophil count \geq 1000/mm³
 - Platelets \geq 90,000/mm³
 - total bilirubin <3X ULN for age
 - AST(SGOT) & ALT(SGPT) \leq 10X institutional upper limit of normal for age
 - Urinalysis no greater than 1+ hematuria or proteinuria
Adults(age18 or >): Serum creatinine \leq 1.2 mg/dl; if serum creatinine is >1.2 mg/dL, nuclear GFR will be measured.
GFR will need to be \geq 80 ml/min/1.73m² for subjects \leq 40 years old,
 - Renal function* \geq 70 ml/min/1.73m² for subjects between 41-50;
 \geq 60 ml/min/1.73m² for subjects between 51-60;
 \geq 50 ml/min/1.73m² for subjects > 60 years old.

Children(age <18): nuclear GFR \geq 80 mL/min/1.73 m²
- * Renal function criteria based on our previous experience with ⁹⁰Y-DOTATOC therapy and known changes in GFR with age^{13,21,33-35}

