7.0 Calendar of Tests and Procedures

Calendar of Tests and Procedures									
Test	Base line ⁶	C1D1 ⁷	C1D2	C2 D1	C2D2	C3D1	C3D2	3-4 Month Followup ^{8, 11}	6-9 Month Followup
Physical Exam	X	X		X		X		X	X
Medical history/treatment history	X	X							
Vital signs ¹	X	X	X	X	X	X	X	X	X
Medication list	X	X		X		X		X	X
GFR if indicated ²	X	X		X		X		X ¹²	X
Blood Tests ³	X	X	X ¹⁴	X	X ¹⁴	X	X ¹⁴	X	X
QOL questionnaire	X	X						X ¹³	
Pregnancy Test ⁴	X	X ⁹	X ⁹	X	X ⁹	X	X ⁹		
⁶⁸ Ga-DOTATOC (TATE) PET/CT	X								X
Diagnostic CT or MRI	X							X	X
⁹⁰ Y-DOTATOC Therapy (& Amino Acids)			X		X		X		
Skin assessment ¹⁵			X		X		X		
Dosimetry (blood & imaging)			X		X		X		
Adverse Event Assessment	X ⁵	X	X	X		X		X	X
Fluid diary ¹¹		X	X	X	X	X	X		

1. temp, pulse, respirs, b/p, weight. Height at baseline only. Weight at baseline and Day 1 of each cycle.

2. required for children(<18 years). Required for adults (18 and older) if serum creatinine >1.2mg/dl. If required at baseline for patient, then all subsequent time points require nuclear GFR also.

3. blood tests include: CBC/diff, AST, ALT, creatinine, plus urinalysis at baseline only and T.Bili at baseline only.

4. required for females of child bearing potential only

5. Documentation of baseline symptoms

6. All baseline evaluations within 30 days of first ⁹⁰Y-DOTATOC dose except blood tests need to be within 10 days and ⁶⁸Ga-DOTATOC/TATE PET/CT needs to be within 6 months of first ⁹⁰Y-DOTATOC infusion. The diagnostic scans need to be within 120 days of the first ⁹⁰Y-DOTATOC infusion.

7. events only repeated prior to treatment 1 if they fall outside of the baseline windows noted in footnote 6.

8. Patients who discontinue dosing of ⁹⁰Y-DOTATOC early and who have received at least 1 dose of ⁹⁰Y-DOTATOC are also required to complete follow up appointments per calendar

9. repeat testing can be point of care urine pregnancy test done in Nuclear Medicine.
10. Patients will be instructed to have fluid intake of 1.5 liters Day 1 and 2 liters/day on Days 3 & 4.
11. 3-4 month follow up procedures may be performed by patient's local MD.
12. If GFR is indicated, patients will be required to return to UIHC.
13. If patient does not return to UIHC for F/U, QOL may be mailed or e-mailed to patient.
14. Electrolytes will be drawn during the last hour of amino acid infusion.
15. The skin at the site of the infusion will be assessed by clinic visit or phone at 3-5 days following each infusion of amino acids.

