10.0 Dosing Delays/Dose Modifications

10.1 Dosage Modifications

Dosimetry will be acquired following treatments 1 & 2. The kidney dose/mCi will be calculated and the total target dose that will limit renal dose to ≤ 23 Gy. The target dose minus 120 mCi will then be divided into two equal doses for Cycles 2 and 3 with adjustments based on dosimetry. Regardless of the total dose to kidneys as determined by dosimetry, the maximum dose in Cycle 2 will be 150 mCi; Cycle 3 will be limited to \leq Cycle 2.

Dose of ^{90}Y -DOTATOC will be decreased 25-50% for any subject in whom dosimetry measurement on first or second dose indicates probable total renal dose for three cycles will be >23 Gy. Dose may be increased on subsequent cycles so long as summation of dosimetry measurements limits total renal dose to ≤ 23 Gy.

Dose of ^{90}Y -DOTATOC will be increased 10-20% for any subject in whom dosimetry measurement on first or second dose indicates probable total renal dose for three cycles will be significantly <23 Gy. No subject will receive > 420 mCi total dose of ^{90}Y -DOTATOC.

Subjects who had a nuclear GFR measured at baseline will be followed for nephrotoxicity by nuclear GFR. If they demonstrate a $\geq 30\%$ decrease in GFR as determined by nuclear GFR scan, their dose will be reduced by 50% on the next cycle. Full dose may then be given when GFR returns to 90% of baseline. Patients who experience $\geq 30\%$ decrease in GFR will be placed on an age appropriate dose of captopril or other ACE inhibitor.

Also, patients that experience a rise in serum creatinine above 1.2 (who previously had normal levels) will be hydrated and have their serum creatinine repeated. If the creatinine level after hydration remains

elevated above 1.2, then nuclear GFR will be measured. If applicable, dose reductions will be implemented as described above.

Nephrotoxicity as demonstrated by $\geq 50\%$ decrease in nuclear scan GFR will be considered a DLT if the resulting GFR is below normal for subject's age, height and weight. Subjects who experience a DLT are eligible to receive subsequent cycles of ^{90}Y -DOTA-tyr³-Octreotide at a reduced dose if the DLT has returned to baseline value within 9 weeks of the intolerated ^{90}Y -DOTA-tyr³-Octreotide dose. The subject's subsequent dose must be reduced to 50% of the intolerated dose.

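### Section 10.1's percent-loss GFR criteria have no reference value in adults with baseline creatinine at or below 1.2 mg/dL, and Section 12.2 plans no renal analysis that would show the loss

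*Combined protocol and SAP*

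**What the plan says.** **Who gets a nuclear GFR.** Section 5.1 accepts adults on creatinine at or below 1.2 mg/dL; "if serum creatinine is >1.2 mg/dL, nuclear GFR will be measured". Footnote 2 of the Section 7.0 calendar requires the scan in all children and says of adults: "Required for adults (18 and older) if serum creatinine >1.2mg/dl". It adds: "If required at baseline for patient, then all subsequent time points require nuclear GFR also". Section 10.1 agrees: "Subjects who had a nuclear GFR measured at baseline will be followed for nephrotoxicity by nuclear GFR". The schema at the front of the protocol and the one in Section 6.0, however, list GFR at every cycle and at follow-up with no condition.

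**What the criteria use.** In Section 10.1, a fall of 30% or more triggers the dose rule: "decrease in GFR as determined by nuclear GFR scan, their dose will be reduced by 50% on the next cycle". At 50% or more, a "decrease in nuclear scan GFR will be considered a DLT if the resulting GFR is below normal" for the subject's age, height and weight. Two recovery rules in the same section also refer to baseline: full dose is allowed again at 90% of baseline GFR, and retreatment after a DLT needs a return to the baseline value.

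**The fallback.** For adults who started with normal creatinine, "patients that experience a rise in serum creatinine above 1.2 (who previously had normal levels) will be hydrated" and retested. If the value stays above 1.2, a nuclear GFR is measured and, where applicable, the dose reductions given earlier in the section are applied.

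**The objective and its analysis.** Primary Objective 2 begins: "Monitor renal, hematologic, and clinical toxicities associated with dosimetry-guided". Section 12.2 analyses it as a table of adverse events by type and grade, with a stopping rule at four or more subjects with renal toxicity of Grade 4 or above.

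**The concern.** A percent decrease needs two measurements. For adults entering at or below 1.2 mg/dL the plan provides at most the second one, so the Section 10.1 rules cannot be applied to them as written. The fallback sends them back to those same rules without naming a reference.

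A second gap lies in the analysis. Until creatinine passes 1.2 mg/dL and stays there, these adults have no GFR-based measure at all, and a fixed threshold means very different things at different starting values. Section 12.2 contains no change-from-baseline analysis of creatinine or GFR. Section 9.1 records a laboratory value as an adverse event only if the investigator considers it clinically important, and it ends routine collection 30 days after treatment (9.1.3 and Appendix II put it at 27 days). Section 9.2 warns that kidney damage can appear months after the last dose.

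At stake is the trial's ability to describe renal loss in the organ that Section 1.4 names as most at risk, and to show that dosing to a 23 Gy renal limit protects it (Hypothesis 2 and Primary Objective 2).

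**Working it through.** No sample size, power or event count in the plan rests on the GFR criteria, so there is no stated figure to reproduce. The check has two parts.

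**1. Which subjects have a reference value**

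| Group | Baseline nuclear GFR (5.1; 7.0 footnote 2) | Later nuclear GFR | Percent decrease computable? |
|---|---|---|---|
| Children | Yes | Every scheduled GFR visit | Yes |
| Adults, creatinine above 1.2 | Yes | Every scheduled GFR visit | Yes |
| Adults, creatinine 1.2 or below throughout | No | None | No |
| Adults, creatinine 1.2 or below, later persistently above | No | After hydration and retest | No |

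The decrease is 1 − G1/G0. In the last row G1 exists and G0 does not. The 30% rule, the percent half of the DLT rule and both recovery rules are therefore undefined. Only the below-normal half of the DLT rule can be judged. If the unconditional schema entries governed, every adult would have a GFR at Cycle 1; but 5.1, 7.0 and 10.1 all say otherwise, so the documents conflict.

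**2. How much loss fits below the 1.2 mg/dL gate**

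Assumption, not in the documents: within a subject, GFR is proportional to creatinine^−e, with e = 1.0 and a range of 0.8 to 1.2.

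- Loss when creatinine reaches 1.2 from baseline b: 1 − (b/1.2)^e
- Highest baseline from which a loss L leaves creatinine at or below 1.2: b = 1.2 × (1 − L)^(1/e)

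| Baseline (mg/dL) | Loss at 1.2, e = 0.8 | e = 1.0 | e = 1.2 |
|---|---|---|---|
| 0.6 | 42.6% | 50.0% | 56.5% |
| 0.7 | 35.0% | 41.7% | 47.6% |
| 0.8 | 27.7% | 33.3% | 38.5% |
| 0.9 | 20.6% | 25.0% | 29.2% |
| 1.0 | 13.6% | 16.7% | 19.7% |
| 1.1 | 6.7% | 8.3% | 9.9% |

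Cut-off baselines:

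- L = 30%: 1.2 × 0.70 = 0.84 for e = 1.0; 0.77 for e = 0.8; 0.89 for e = 1.2.
- L = 50%: 1.2 × 0.50 = 0.60 for e = 1.0; 0.50 for e = 0.8; 0.67 for e = 1.2.

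From baselines of about 0.9 mg/dL upward, the gate acts at or before roughly 30% loss across the whole range of e. The blind spot is at the low end only.

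**The case against.** The strongest reply is that Section 10.1 governs dosing, not the endpoint. Primary Objective 2 is analysed by CTCAE grade under 12.2, which needs no nuclear GFR. Creatinine is in the blood panel at baseline, at Day 1 of each cycle (Cycle 1 only if the baseline value is out of window) and at both follow-ups. Protection does not depend on the gate alone either. Renal dosimetry can lower the dose in any subject under 10.1, and 8.1 stops treatment when the cumulative renal dose exceeds 23 Gy, for unacceptable toxicity such as irreversible renal damage, or on the investigator's judgment. Serious events beyond 30 days are still reported if at least possibly related. All of this stands.

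It rules out two stronger readings. A reader might infer that renal toxicity goes largely unmeasured in these adults; the creatinine schedule and CTCAE grading contradict that. A reader might also infer that the reported renal toxicity rate is necessarily biased low. That does not follow, because the 10.1 triggers are not the 12.2 endpoint and the documents do not reproduce the CTCAE creatinine criteria that would decide which rises are graded.

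The reply leaves two things untouched. A stated rule still cannot be computed for a defined group of subjects. And creatinine collected at 3–4 and 6–9 months still has no planned analysis, while its route into the adverse-event table depends on individual judgment.

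**Conclusion.** The point holds in a limited form. For adults with baseline creatinine at or below 1.2 mg/dL, the percent criteria and the return-to-baseline rules in 10.1 cannot be evaluated, even after the fallback scan. This follows from the text alone.

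The insensitivity of the gate is an illustration. Under the stated power relation, 30% of GFR can be lost without crossing 1.2 mg/dL from baselines up to about 0.84 (0.77 to 0.89), and 50% from up to about 0.60 (0.50 to 0.67). It would be wrong to call the latter a missed DLT: the definition also requires a GFR below normal, and nothing in the documents shows that such an adult would meet that condition. The documents do not give the distribution of baseline creatinine, so the number affected is unknown.

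For the analysis, the supportable conclusion is that such losses may fail to appear in the Primary Objective 2 tables, not that they will. The plan should be changed on this point, since the trial already collects the data needed.

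**What to change.** **Analysis (12.2).** Add a descriptive renal safety endpoint for all adults: percent change from baseline in creatinine-based estimated GFR, at Day 1 of Cycles 2 and 3 and at the 3–4 and 6–9 month follow-ups. Define baseline as the last creatinine before the first infusion. Name an age-appropriate equation in advance. Tabulate the numbers with a loss of 30% or more and of 50% or more at each visit and at any visit, with the number having a value as denominator.

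**Wording.** The two schemas, 5.1, 7.0 footnote 2 and 10.1 must be reconciled on who has a baseline GFR, and on what reference applies when nuclear GFR is first measured on study. That choice belongs to the investigators; no dose or clinical rule is proposed here.

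**Cost.** Creatinine is already scheduled at these visits, so the analysis needs no extra scan or blood draw. Day 2 bloods are electrolytes and are not used. Estimated GFR is less precise than nuclear GFR, and the 3–4 month sample may be taken by a local physician, so the endpoint should be labelled descriptive and kept apart from the 10.1 criteria. It does not supply the missing nuclear GFR reference; only the reconciliation can settle that.

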10.2 Dose Delay

The time elapsed between the end of week 6 of a Cycle Study Period and Day 1 of the next Cycle Study Period should be ≤ 3 weeks. No further interruption between cycles should occur, except delays mandated by the protocol itself or regulatory requirements as in periods of enrollment locks or data review by health authorities. If a longer interruption does occur, the subject's continuation will be at the discretion of the Principal Investigator; approval will not be unreasonably withheld.

10.3 Concomitant Therapy

The subject may not receive any other approved or investigational anti-neoplastic therapies for the treatment of the refractory somatostatin-receptor positive tumor during the course of the study, excluding somatostatin analogues and bisphosphonates. However, all subjects on somatostatin analogue therapy will discontinue therapy from 12 hours prior to a) injection with ^{68}Ga -DOTATOC, and b) infusion with ^{90}Y -DOTA-tyr³-Octreotide until 12 hours post administration. Subjects who have been on hormonal therapy (other than somatostatin analogues) for ≥ 2 months with SD or PD may continue to receive hormonal therapy during this study. Subjects who initiate another tumor-specific therapy will be discontinued from further treatment with ^{90}Y -DOTA-tyr³-Octreotide. Patients may continue long acting Somatostatin analogues between cycles of ^{90}Y therapy. It should be administered as standard of care after completion of dosimetry imaging for Cycles 1 and 2. Following Cycle 3, it may be given on Day 3 or later. Patients on long acting Lanreotide should have this treatment held until after ^{90}Y treatment Cycle 3. Short acting somatostatin analogue can be used at the discretion of the treating physician to bridge the patient.

All subjects who have received at least one dose of ^{90}Y -DOTA-tyr³-Octreotide must continue into the Long-Term Follow-up Study Period at the point of treatment discontinuation. This is necessary to determine any long-term effects of treatment with ^{90}Y -DOTA-tyr³-Octreotide.

Subjects may receive, at the discretion of the investigator, appropriate medical treatment for medical problems that arise while on study.

11.0 Response Criteria/End of Study Assessments

11.1 Response criteria according to RECIST 1.1 include:

	Evaluation of Target Lesions
Complete Response (CR):	Disappearance of all target lesions. Any pathological lymph nodes (whether target or non-target) must have reduction in short axis to <10 mm.
Partial Response (PR):	At least a 30% decrease in the sum of the diameters of target lesions, taking as reference the baseline sum diameters

Progressive Disease (PD):	At least a 20% increase in the sum of the diameters of target lesions, taking as reference the smallest sum on study (this includes the baseline sum if that is the smallest on study). In addition to the relative increase of 20%, the sum must also demonstrate an absolute increase of at least 5 mm. (Note: the appearance of one or more new lesions is also considered progressions).
Stable Disease (SD):	Neither sufficient shrinkage to qualify for PR nor sufficient increase to qualify for PD, taking as reference the smallest sum diameters while on study
Evaluation of Non-Target Lesions	
Complete Response (CR):	Disappearance of all non-target lesions and normalization of tumor marker level. All lymph nodes must be non-pathological in size (<10 mm short axis)
	Note: If tumor markers are initially above the upper normal limit, they must normalize for a patient to be considered in complete clinical response.
Non-CR/Non-PD:	Persistence of one or more non-target lesion(s) and/or maintenance of tumor marker level above the normal limits
Progressive Disease (PD):	Appearance of one or more new lesions and/or unequivocal progression of existing non-target lesions. Unequivocal progression should not normally trump target lesion status. It must be representative of overall disease status change, not a single lesion increase.

12.0 Data Analysis and Statistics:

12.1 Primary Objective 1

Treatment efficacy, defined as a complete response, partial response or stable disease (CR+PR+SD), is the primary endpoint of interest in this dosimetry-guided Phase II trial. Tumor response will be defined according to RECIST1.1 criteria applied on up to five target lesions (primary tumor if not surgically removed, up to two liver lesions, up to two nodal metastases, metastatic lesion in other organs, such as ovary, breast) that will be quantified and compared between pre-therapy and 3-9 months post-therapy high-resolution, contrast-enhanced CTs. Osseous metastases may be followed as non-target lesions. ⁹⁰Y-DOTATOC will be deemed worthy of further study if its associated response rate is ≥ 0.60 , and clinically uninteresting if its rate is ≤ 0.40 . Enrollment will proceed according to an optimal Simon two-stage study design. Sixteen (16) subjects will be enrolled in the first stage; if 7 or fewer patients respond, the arm will be closed and the treatment ruled clinically uninteresting. Otherwise, an additional 30 subjects will be enrolled. If 24 or more responses are observed in the total of 46 subjects, then the treatment will be ruled worthy of further study. The study design has a probability of early termination equal to 0.72. Power to detect efficacy is 0.80 with a type 1 error rate of

0.05.

Secondary analysis will focus on time to tumor progression and overall survival. The method of Kaplan- Meier will be used to estimate progression and survival rates. Subjects for whom the outcome of interest is not observed at the 6 month follow-up will be treated as censored observations in the survival analysis.

12.2 Primary Objective 2

Adverse events will be recorded and reported in tabular form by type and grade. If four or more subjects experience renal toxicity \geq Grade 4, the radiopharmaceutical will be declared too toxic and the trial will be stopped. If any other irreversible Grade 4 toxicity is observed in four or more subjects, the treatment will be declared too toxic and will be stopped. Adverse events will be graded according to the most recent CTE guidelines.

12.3 Secondary Objective 1

For subjects who participated in the ^{68}Ga -DOTATOC Comparator trial (IRB # 201212736), the number, size, and location of discordant lesions between ^{68}Ga -DOTATOC PET/CT and Octreoscan will have been tabulated. This analysis will be updated using the results of post- therapy ^{68}Ga -DOTATOC PET/CT for those patients who participated in the comparator study, but only received the initial ^{68}Ga -DOTATOC PET/CT due to progression on the Octreoscan + high-resolution, contrast-enhanced CT. Lesions that were positive on PET, but negative on Octreoscan will be considered true positive if a response to PRRT is documented after either Cycle 1 or at 6-9 month followup following last ^{90}Y -DOTATOC infusion.

For subjects who did not participate in the ^{68}Ga -DOTATOC Comparator trial, all ^{68}Ga -DOTATOC PET/CT scans will be acquired as part of this study; number, size, and location of lesions will be analyzed between first and subsequent ^{68}Ga -DOTATOC PET/CTs.

12.4 Secondary Objective 2

Compare SUVmax between primary tumor, liver lesions, and extra-hepatic lesions with expression levels of sst2 using qRT-PCR and/or receptor IHC from fresh frozen or paraffin-embedded samples where available.

Compare maximum SUVs of primary tumor, liver lesions, and extra-hepatic lesions with expression level of sst2 RNA and IHC on fresh frozen tissue, or paraffin embedded samples (block(s) or 10 unstained slides) to determine whether or not any correlation exists between SUVmax, sst2 expression, or sst2 protein and response to PRRT. The study is expected to delineate whether measurement of sst2 expression by either qRT-PCT or immunohistochemistry at diagnosis can predict response to ^{90}Y -DOTATOC. We will construct a table tabulating SUVmax, level of RNA expression, and IHC level for all lesions biopsied. With 64 subjects the correlation between SUV max, RNA expression and IHC will be determined. Analysis of SUVmax compared with sst2 RNA and receptor protein expression on primary tumor and metastatic lesions will be considered worthy of further study if $> 50\%$ of lesions demonstrate a positive correlation. Tissue will be sent to 3080 Med Lab in University of Iowa Hospital and Clinics for analysis.

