6.0 Imaging and Treatment Plan

**Phase II,
Dosimetry-Guided, Peptide Receptor Radiotherapy (PRRT) with
⁹⁰Y-DOTA-tyr³-Octreotide (⁹⁰Y-DOTATOC) in Children and Adults
with Neuroendocrine and other Somatostatin Receptor Expressing Tumors**

Treatment Cycles and Followup		Imaging and Treatment Schedule	Initial ⁹⁰ Y-DOTATOC Dose	Cumulative ⁹⁰ Y-DOTATOC Dose	Cumulative Renal Radiation
Cycle 1 Week 1	Day 1	Physical exam with height, weight, vitals, labs, list, GFR, pregnancy test; QOL questionnaire Start 18 hrs IV/PO fluids			
	Day 2	⁹⁰ Y-DOTATOC + IV amino acids Continue IV/PO fluids for 48 hrs	50 mCi/m ² in children; 120 mCi in adults	120 mCi maximum	
	Day 4	⁹⁰ Y-DOTATOC PET/CT			
Cycle 2 Week 7-9	Day 1	Physical exam with height, weight, vitals, labs, med list, GFR, pregnancy test Start 18 hrs IV/PO fluids			
	Day 2	⁹⁰ Y-DOTATOC + IV amino acids Continue IV/PO fluids for 48 hrs	Dosimetry determined	270 mCi maximum	
	Day 4	⁹⁰ Y-DOTATOC PET/CT			
Cycle 3 Week 13-17	Day 1	Physical exam with height, weight, vitals, labs, list, GFR, pregnancy test Start 18 hrs IV/PO fluids			
	Days 2-3	⁹⁰ Y-DOTATOC + IV amino acids Continue IV/PO fluids for 48 hrs	Dosimetry determined	420 mCi maximum	≤ 23 Gy
FU	3 months after treatment 3	Physical exam with height, weight, vitals, labs, med list, GFR; QOL questionnaire, diagnostic CT (MRI)			
	6-9 months after treatment 3	Physical exam with height, weight, vitals, labs, med list, GFR; diagnostic CT (MRI) ⁶⁸ Ga-DOTATOC PET/CT;			

Treatment consists of 3 cycles, 6-8 weeks apart. Cycle 1 dose is fixed. Cycles 2 and 3 doses will be determined by dosimetry-based calculation of renal doses from previous cycles; total renal dose ≤ 23Gy.

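### The response window appears to run from the last infusion, so a patient who stops early is judged for stable disease 6 to 16 weeks sooner after Cycle 1 than a completer at the same visit

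*Combined protocol and SAP*

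**What the plan says.** Section 12.1 sets treatment efficacy, "defined as a complete response, partial response or stable disease (CR+PR+SD), is the primary endpoint of interest". Target lesions are those "that will be quantified and compared between pre-therapy and 3-9 months post-therapy high-resolution, contrast-enhanced CTs". Section 11.1 defines SD as "Neither sufficient shrinkage to qualify for PR nor sufficient increase to qualify for PD", with no minimum duration.

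The anchor for the scan is stated in different ways:

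- The Section 6.0 schema places the first follow-up CT "3 months after treatment 3" and the second 6-9 months after treatment 3. The Section 7.0 calendar labels these visits 3-4 and 6-9 months. Both include a diagnostic CT or MRI.
- Footnote 8 of the calendar says that patients who stop early after at least one dose "are also required to complete follow up appointments per calendar".
- Section 10.3 says that all subjects given at least one dose "must continue into the Long-Term Follow-up Study Period at the point of treatment discontinuation".
- Hypothesis 3 in Section 3.1 and the analysis in Section 12.3 time response from the last infusion.

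On timing, Section 6.0 says "Treatment consists of 3 cycles, 6-8 weeks apart". Section 10.2 adds "The time elapsed between the end of week 6 of a Cycle Study Period and Day 1 of the next Cycle Study Period should be" no more than 3 weeks. Footnote 6 allows the baseline CT up to 120 days before the first infusion. Section 8.1 lists reasons for stopping that are not tumour growth, such as the cumulative renal dose, toxicity and withdrawal, and says that progression alone does not require a stop.

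**The concern.** A patient with one or two cycles has no treatment 3, so the schema's anchor cannot apply. The remaining text points to the last infusion. The time over which a patient must remain free of progression then depends on how many cycles were given. Since not having progressed counts as success, less treatment brings an earlier and easier test.

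At stake is what the 7/16 and 24/46 boundaries measure. If some subjects are read well before others, the success count mixes disease control at different times and can exceed the rate at any common time. No section names the scan that decides the endpoint or says how an early stopper is scored.

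**Working it through.** **The plan's own figures.** With X ~ Bin(16, p) and Y ~ Bin(30, p), P(early stop) = P(X ≤ 7) and P(pass) = Σ over x = 8 to 16 of P(X = x) × P(Y ≥ 24 − x). At p = 0.40, P(early stop) = 0.716 and P(pass) = 0.0486. At p = 0.60, P(pass) = 0.8006. Section 12.1's 0.72, 0.05 and 0.80 reproduce. (Section 8.2 gives a different two-stage rule, 35 then 64 subjects. The two must be reconciled, but that is a separate matter.)

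**Elapsed time from Cycle 1 to the scan.** Cycles 6-8 weeks apart put Cycle 3 at 12-16 weeks after Cycle 1. One month is 52.18/12 = 4.35 weeks. Ratio = stopper's time / completer's time. The last column adds a baseline CT taken 120 days (17.1 weeks) before Cycle 1 to both.

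| Scan after last infusion | One-cycle stopper | Completer | Ratio | Ratio with 120-day lead |
|---|---|---|---|---|
| 3 months | 13.0 wk | 25.0-29.0 wk | 0.45-0.52 | 0.65-0.72 |
| 4 months | 17.4 wk | 29.4-33.4 wk | 0.52-0.59 | 0.68-0.74 |
| 6 months | 26.1 wk | 38.1-42.1 wk | 0.62-0.68 | 0.73-0.78 |
| 9 months | 39.1 wk | 51.1-55.1 wk | 0.71-0.77 | 0.78-0.82 |

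With the longest delays that Section 10.2 allows, Cycle 3 falls at 18 weeks and the 3-month ratio drops to 13.0/31.0 = 0.42. A two-cycle stopper is read 6-8 weeks sooner than a completer.

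**Illustrative effect on the 16/46 rule.** Assumptions, none of them in the documents: 10, 20 or 30% stop early, half after each cycle; the progression hazard is constant and the same in stoppers and completers; success is driven by SD; there is no baseline lead. Midpoints are Cycle 3 at 14 weeks (3.22 months) and scans at 3.5 and 7.5 months after the last infusion.

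- First scan: one-cycle 3.50, two-cycle 5.11, completer 6.72 months from Cycle 1. If the rate at 6.72 months is 0.40, one-cycle stoppers score 0.40^(3.50/6.72) = 0.620 and two-cycle stoppers 0.40^(5.11/6.72) = 0.498, mean 0.559. The overall rate is 0.40 + f × 0.159 = 0.416/0.432/0.448. P(pass) = 0.074/0.109/0.153.
- Second scan: 7.50, 9.11 and 10.72 months. Stoppers score 0.527 and 0.459, mean 0.493. The overall rate is 0.409/0.419/0.428. P(pass) = 0.063/0.079/0.099.
- With a 120-day baseline lead for everyone: 0.063/0.080/0.100 (first scan) and 0.058/0.069/0.082 (second).

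**With the times to progression in Section 1.4.** S(t) = 2^(−t/median). At the first scan, a median of 36 months gives 0.935 (one-cycle) against 0.879 (completer), a gap of 5.6 points; 48 months gives 0.951 against 0.908, or 4.3 points. A median of 6 months, within the 5-7 months quoted for the comparator drugs, gives 0.667 against 0.460, or 21 points.

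**The case against.** **Stoppers may progress faster.** They receive less treatment, and some stop because their condition worsens. A one-cycle stopper's advantage over a completer vanishes at a hazard ratio of about 1.9-2.2 (3-month scan), 1.5-1.6 (6 months) or 1.3-1.4 (9 months). If completers are held at 0.40 and stoppers' hazard is doubled, P(pass) falls to 0.038/0.030/0.023 at the first scan. This stands against a reading that someone might draw from the timing, that early stoppers as a group outscore completers or that the success count must rise with discontinuation. It does not remove the timing effect, because the relevant comparison is the same stoppers read at the common time. With the overall common-time rate fixed at 0.40 and hazard ratios from 1 to 2, P(pass) is 0.074-0.076/0.109-0.113/0.153-0.160 at the first scan and 0.062-0.063/0.078-0.080/0.099-0.101 at the second.

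**The null is not a fixed-time rate.** Section 12.1 sets 0.40 as the response rate under its own endpoint. If the rate so scored is 0.40, P(pass) is 0.0486. This stands: the documents do not show that the stated 0.05 is breached. The issue is what is being estimated.

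**Half the time is a corner case.** A reader may infer that early stoppers generally have about half the completers' time. That fits only one-cycle stoppers at the first scan, counted from Cycle 1. Later scans, two-cycle stoppers and a baseline lead all move the ratio toward 1.

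**Stopping may be rare, and the anchor is inferred.** The documents give no stopping rate. Section 10.1 adapts doses rather than ending treatment, and Sections 1.5 and 13.3 report little serious toxicity before. Section 10.3's stated purpose is long-term effects, not response timing. These points limit the size and certainty, but no section gives a different anchor that an early stopper could use.

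**Conclusion.** The point holds in a limited form. As the text reads, a one-cycle patient is judged 12-16 weeks sooner after Cycle 1 than a completer at the same visit, and a two-cycle patient 6-8 weeks sooner. Because SD counts with no minimum duration, the same patient is more easily a success on the shorter interval, and the success count can exceed the disease-control rate at a common time.

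The size is conditional. The pass probabilities of about 0.07/0.11/0.15 (first scan) or 0.06/0.08/0.10 (second), against 0.049, rest on assumed stopping rates, a constant hazard and no baseline lead. The effect matters when the true rate lies near the boundary. If times to progression are as long as Section 1.4 reports for this treatment class, the stopper-completer gap is about 6 points or less and completers' disease control would lie well above 0.60. This is a cheap improvement to the definition of the endpoint, not a demonstrated failure of the design.

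**What to change.** In Section 12.1, name the one CT/MRI that decides the primary endpoint and time it from the Cycle 1 infusion for every treated subject, at the completers' elapsed time: about 25-34 weeks if the first scan decides, about 38-55 weeks if the second does. Align footnote 8, Section 10.3 and the schema so that early stoppers have that response scan in the same window. State that documented progression by then, or no evaluable scan in the window, counts as non-response. Leave safety visits as they are.

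Naming the scan also narrows the spread among completers, which is now 25-55 weeks.

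The cost is wording in four places, with no added scans. Early stoppers' response scan moves up to about 3-4 months later, and a few more of them may be lost or start another therapy first. The plan should say how those who start another therapy before the scan are scored.
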